Patient Selection: 276 parents of Medicaid-insured children ages 2-12 years inclusive, seeking asthma care at Seattle Children’s or Mary Bridge Children’s emergency department who are the primary owners of a mobile phone with text messaging service.

Outcomes: Outcome data on parental self-efficacy and outcome expectations, adherence to asthma care treatment recommendations (e.g. primary care utilization), and child

asthma outcomes (e.g., ED visits, asthma morbidity) will be collected via structured telephone interviews at 3, 6, 12, 18, and 24 months post- enrollment.

Study Aims & Hypotheses

Aim 1: To improve urban, low-income children’s asthma-related health outcomes (primary outcome: reduced ED visits for asthma care, secondary outcome: lower morbidity) over 12 months.

Hypothesis 1a: Children of parents who receive T2B will make fewer ED visits for asthma care than those receiving standard ED asthma care alone.

Hypothesis 1b: Parents who receive T2B will report lower morbidity (i.e., days of impairment) than those receiving standard care.

Aim 2: To improve adherence to asthma care guidelines (primary care utilization for asthma care and improved parent asthma care self-management) over 12 months.

Hypothesis 2a: Parents who receive T2B will report increased primary care utilization (i.e., more frequent follow-up with their child’s PCP for routine asthma care) than those receiving standard care.

Hypothesis 2b: Parents who receive T2B will demonstrate greater knowledge of asthma self-management than those receiving standard care.

Hypothesis 2c: Primary care utilization and improved self-management will mediate the effect of T2B on children’s asthma-related health outcomes.

Aim 3: To improve parent cognitions (parental self-efficacy and outcome expectations) regarding partnering with their child’s PCP for asthma care over 12 months.

Hypothesis 3a: Parents who receive T2B will report greater self-efficacy in communicating with their child’s PCP about their child’s asthma care and greater outcome expectations for effective treatment and control of their child’s asthma symptoms than those receiving standard care.

Hypothesis 3b: Parental self-efficacy and outcome expectations will mediate the effect of T2B on adherence to asthma care guidelines.

Background and Study Rationale

Pediatric Asthma Epidemiology

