the primary owners of a mobile phone with text messaging service, which is anticipated to be at least 75% of parents in this population based on previous research on urban, low-income parents.^{59, 60}

Exclusion criteria: Parents of children with significant medical co-morbidities (e.g., sickle cell disease, insulin-dependent diabetes mellitus) will be excluded because of their increased interaction with healthcare providers.

Recruitment and Randomization

CRA's will identify potentially eligible patients through electronic admission board and medical record diagnostic codes after intake into the ED, and they will describe the study to potentially eligible parents while they are waiting to be seen by a provider. Interested families will be screened for eligibility. If eligible, parents will complete the consent process. (See section 5.2.a for more details.) Then the CRA will administer a baseline questionnaire focusing on health care utilization, asthma self-management and morbidity, parental self-efficacy and outcome expectations. After the questionnaire is completed, participants will be randomized to usual care or the intervention group (T2B). Randomization will occur automatically via the RedCap database system. Time allowing, participants randomized to the intervention will receive brief education on the 3 S's and orientation to the text message component (including an "opt-in" code) while in the ED or if necessary by phone within 48 hours. The text message education component will begin within 1 week after participants are randomized, allowing time for participants to enter the opt-in code.

Retention and Compensation

Parents will receive total compensation of \$110 for participation in the study to be dispensed as: \$20 gift card will be given to the parent after he/she completes the baseline interview and \$30 gift cards will be sent after the 3, 6, 12 follow-up interviews; Based on previous studies conducted by our research team with similar populations, this amount should be sufficient to compensate participants for their time and offset the cost incurred for the text messages (if any), but it will not be coercive, minimizing participation solely based on financial gain.

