To assist with subject retention, considering the transient nature of this community and the fact that phone numbers are frequently disconnected and/or changed, we will obtain up to 3 contacts' phone numbers from each participant at enrollment, and review and update contacts at each follow-up interview. Using this method in previous studies, our research team has successfully maintained 90% subject retention at 6-month follow-up.¹⁵ In addition, Rip Road has extensive experience working with underserved populations [through public health departments] and pay-as-you-go service providers, and can thus nimbly respond and adapt to

any service interruptions. The window for follow up visits will be two weeks prior and post the due date for the 3 and 6 month follow up time points and 1 month prior and post the due date for 12month follow up time point. To enhance our ability to retain participants for, at each wave of follow-up, the system will send text message reminders to participants to alert them that their follow-up call is approaching and to contact the study coordinator to schedule. If a call has not already been scheduled as of day 1 of the open window, a CRA will contact the family. If no contact has been made as of the due date an online version of the follow up survey will be emailed to the provided email contact. If the participant misses a wave they will still be called for the next follow-up. Information for alternative contacts will also be collected at the time of consent. These contacts will be utilized when participants' provided phone numbers are inactive.

Data Collection

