Trained CRAs will conduct structured in-person interviews after participants have consented and before randomization. Follow-up interviews, lasting approximately 30 minutes, will be conducted by a trained CRA blinded to participants' randomization. In cases when no blinded CRA is available an unblinded CRA may complete the survey. Unblinded status will be documented for each survey conducted. Electronic medical record review will be conducted by trained study staff at the site where the participant was enrolled. Measures of asthma outcomes for this study are aligned with the recent recommendations of the Asthma Outcomes Groups for standardization of definitions and data collection methodologies for asthma research studies and clinical trials.^{75,76} All, but one of the following measures will be administered at each wave of data collection. The Asthma Self-Management Questionnaire will be administered at baseline and 12 months. (see appendix for Baseline Survey).

Distal Outcome Measures – Child Asthma Outcomes

ED visits for asthma care: Parents will report whether and how many times their child was taken to the emergency room because of asthma during the past 12 months using 2 questions administered in several national-scale surveys;⁷⁵ they will also indicate whether those visits included receipt of systemic corticosteroids.⁷⁶ We will validate a large portion of this data with EMR review because Seattle Children's is the primary ED utilized by young patients in the Seattle area and Mary Bridge Children's the primary ED utilized by young patients in the Tacoma area.

Asthma Morbidity: Asthma morbidity will be assessed by the questions used in the Inner City Asthma Consortium (ICAC)^{73, 74, 77, 78} and applied subsequently in numerous studies, including the study validating the IMPACT DC intervention.¹⁵ Morbidity will be measured as the number of days (or nights) of impairment in the prior 2 weeks.

Proximal Outcome Measures – Adherence to Treatment Recommendations

Primary Care Utilization: To maintain continuity in outcomes with the IMPACT DC RCT,¹⁵ we will ask parents to identify their child’s primary asthma health care provider, as well as their child’s primary care provider. A computed variable will indicate whether the named PCP is the child’s primary asthma health care provider. In addition, we will ask parents about frequency of PCP visits for asthma care at each telephone follow-up interview.

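### The stated ED-visit question looks back over a rolling 12 months, so a 12-month call made before the anniversary can count the enrolment ED visit in both arms and pull the primary rate ratio toward 1

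*Protocol*

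**What the plan says.** SAP C.5.b (Aim 1) defines the primary outcome as asthma ED visits in the 12 months after randomisation. It is analysed by negative binomial regression with study group as the only independent variable.

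The protocol's Outcomes paragraph says that child "asthma outcomes (e.g., ED visits, asthma morbidity) will be collected via structured telephone interviews". Under Data Collection (Distal Outcome Measures), parents report "how many times their child was taken to the emergency room because of asthma during the past 12 months using 2 questions". The same section states: "All, but one of the following measures will be administered at each wave of data collection". The one exception it names is the self-management questionnaire.

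Medical records have a supporting role: "We will validate a large portion of this data with EMR review". On who does this and where: "Electronic medical record review will be conducted by trained study staff at the site where the participant was enrolled".

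Under Recruitment and Randomization, staff "will identify potentially eligible patients through electronic admission board and medical record diagnostic codes after intake into the ED", and randomisation follows consent and the baseline questionnaire. Under Retention and Compensation, the window for the last call is "1 month prior and post the due date for 12month follow up time point". Staff contact unscheduled families from the first day of that window, and an online survey is emailed if no contact has been made by the due date.

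**The concern.** The question counts backwards from the interview, whereas the endpoint counts forwards from randomisation. The two periods coincide only when the call falls on the anniversary.

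A call held before the anniversary reaches back past randomisation by up to a month, and that stretch contains an event every child has by design: the asthma ED visit at which the family was enrolled. Early calls are a planned route, not a deviation. No passage excludes the enrolment visit, bounds the count by date, or says that record dates override the parent's report.

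Adding about one visit per early-called child to both arms is a large addition against a planned control mean of 1.28. It makes a real benefit look smaller and costs power. It does not create a false benefit.

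A secondary point does not depend on call timing. At 3 and 6 months, about 75% and 50% of a 12-month look-back lies before randomisation, and those waves feed the path and growth models in SAP C.5.b (Aim 2).

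**Working it through.** **Inputs from SAP C.5.c.** Control rate 1.28 per year; 35% reduction, so T2B rate 1.28 × 0.65 = 0.832; two-sided 5%; 125 per group for at least 90% power; analytic sample 110 per group with power above 80%.

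**Assumptions not in the documents.** Pre-randomisation ED rate 1.28 per year; early calls half a month early on average; the same early share in both arms. The share of early calls and the share of parents who count the enrolment visit are varied.

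**The plan's own figure.** n per group = (1.960 + 1.282)² × (1/1.28 + 1/0.832 + 2k) / (ln 0.65)², where k is the negative binomial dispersion. With k = 0 this gives 112.3, so 113. No dispersion is stated, so 125 cannot be reproduced exactly; it corresponds to k of about 0.11. At 110 per group the formula gives 89.4% power for k = 0, 86.0% for k = 0.11, 80.3% for k = 0.3 and 61.9% for k = 1.

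**Expected count at an early call (11.5 months), visit counted.**
- Control: 1.28 × 11.5/12 + 1 + 1.28 × 0.5/12 = 2.280
- T2B: 0.832 × 11.5/12 + 1 + 1.28 × 0.5/12 = 1.851
- Ratio: 1.851/2.280 = 0.812

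Mixing with on-time calls (0.832 and 1.28) gives 1.341/1.780 = 0.754 at 50% early and 1.087/1.530 = 0.710 at 25% early.

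| Expected rate ratio (true 0.65) | 25% early | 50% early | 100% early |
|---|---|---|---|
| All parents count the visit | 0.710 | 0.754 | 0.812 |
| All count, calls a full month early | 0.713 | 0.759 | 0.820 |
| Half count it | 0.684 | 0.713 | 0.759 |
| None count it | 0.654 | 0.657 | 0.665 |

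With no parent counting and every call a full month early, the ratio is 0.869/1.280 = 0.679. Moving the pre-randomisation rate from 0 to 2.56 per year changes the first row by less than 0.01. The enrolment visit therefore drives the result, not the extra time.

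**Simulated power.** 110 per group, all parents counting, 4,000 replicates per cell (Monte Carlo error up to about 1.6 points), gamma frailty shared before and after randomisation, negative binomial fit by maximum likelihood, two-sided Wald test at 5%.

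| Dispersion, standard error | 0% early | 25% | 35% | 50% | 100% |
|---|---|---|---|---|---|
| k = 0, model-based | 89.4 | 82.2 | 80.2 | 76.0 | 64.2 |
| k = 0, empirical | 90.0 | 84.0 | 82.7 | 81.4 | 88.0 |
| k = 0.3, model-based | 80.9 | 74.4 | 73.0 | 71.2 | 61.7 |
| k = 0.3, empirical | 81.0 | 74.3 | 72.8 | 71.9 | 75.8 |
| k = 1, model-based | 62.0 | 58.9 | 59.3 | 57.5 | 58.1 |
| k = 1, empirical | 61.8 | 57.6 | 57.6 | 55.4 | 59.2 |

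A separate, smaller simulation (500 replicates) at k = 0.11 gave 87, 81, 74 and 62% at 0, 25, 50 and 100% early. If no parent counts the visit (k = 0), power is 89.8, 87.9 and 85.8% at 25, 50 and 100% early.

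**No true effect.** Both arms at 1.28, 50% early, 2,500 replicates: the mean ratio is 1.00, with rejection in 3.0, 4.9 and 6.5% of trials for k = 0, 0.3 and 1.

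**3 and 6 months, on-time call.**
- 3 months: control 1.28 + 1 = 2.280; T2B 1.28 × 9/12 + 0.832 × 3/12 + 1 = 2.168; ratio 0.951 (1.168/1.280 = 0.9125 without the enrolment visit).
- 6 months: T2B 1.28 × 6/12 + 0.832 × 6/12 + 1 = 2.056; ratio 2.056/2.280 = 0.902 (1.056/1.280 = 0.825 without it).

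These are indicative only, because the outcome in those models also includes urgent care.

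**The case against.** The endpoint itself is already fixed as visits after randomisation, so in principle the enrolment visit is excluded. That is right, but no procedure links the survey answer to that count, and an answer taken at face value would not match the definition.

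The follow-up form is not in the documents. The protocol refers to an appendix only for the baseline survey, where a past-year question is natural, and the follow-up form may be anchored to enrolment. This stands, and it is why the first step is to check the form. Even so, the protocol says the same measures are given at every wave.

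The enrolment visit took place at the site whose records are reviewed, and its date is known, so it could be removed. This also stands and makes correction feasible. The protocol describes record review only as validation, though, and without a date rule it could simply confirm the enrolment visit as genuine.

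The larger losses need many early calls and most parents counting the visit. First-day contact is an attempt, not a completed interview, so 100% early is an upper bound. If half of parents count the visit (k = 0), power is about 83% at 35% early and 81% at 50%. Much of the loss comes from the model-based standard error, and with strong overdispersion low power is mainly a dispersion problem. All of this limits the size of the power claim. The dilution of the estimate remains.

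Late calls also depart from the defined interval: they lose the first weeks after randomisation and add time beyond month 12. They do not pick up the enrolment visit, and the same date rule covers them.

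**Conclusion.** The concern holds. The protocol's stated ED-visit item does not measure the SAP's primary outcome when the 12-month call comes before the anniversary, and nothing written corrects it. The direction is toward no difference.

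The size is uncertain. A true ratio of 0.65 becomes 0.71 to 0.81 over 25% to 100% early calls if every parent counts the enrolment visit, 0.68 to 0.76 if half do, and stays at 0.65 to 0.68 if none does. The stated power above 80% is lost at about one-third early calls only if there is no overdispersion, every parent counts the visit, and model-based errors are used. With k = 0.3 the margin is already gone: 81% with no early calls and 74% at 25% early.

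All of this assumes similar early-call shares in the two arms; an imbalance could bias the ratio in either direction. Confidence is medium because the follow-up form, call timing and recall are not documented. The point should be fixed, since it bears on the primary estimate and could hide a real benefit.

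**What to change.** 1. Confirm the wording of the follow-up item. If it is already anchored to enrolment, correct the protocol text; the steps below that concern wording and early interviews then fall away.
2. If it is a 12-month look-back, ask at each follow-up about asthma ED visits *since the ED visit when you joined the study, not counting that visit*, or *since our last interview on [date]*.
3. In the SAP, define the primary count operationally: visits dated after randomisation and up to month 12, enrolment visit excluded, with a log(time covered) offset where the interview date sets the period. State how dated record entries are combined with parent reports.
4. For interviews already completed, flag those held before the anniversary and remove the enrolment visit and any earlier visits, using enrolment, interview and record dates.

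The cost is low to moderate: one reworded item, one derivation rule, one offset and a flag on early interviews. No interview has to be repeated. There are two downsides. The item departs from the national-survey wording, and record dates cover only the enrolling site. The second does not hinder removal of the enrolment visit, but it does limit the dating of visits elsewhere.

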Parental Outcome Expectations: In accordance with other research of pediatric asthma interventions, to assess parents’ beliefs about possible asthma quality of life for their child we will administer an 8-item measure of parental expectations for asthma treatment.⁸³ Parents respond to statements about their expectations (e.g., “I believe that my child can be symptom free most of the time.”) using a 5-point Likert scale (1=strongly disagree to 5=strongly agree). Total scores are calculated by averaging across responses, and higher scores reflect more optimistic asthma outcome expectations (Cronbach’s alpha = 0.70).

Study Intervention

The T2B intervention will consist of a personalized, interactive text-messaging program with asthma and health communication education (derived from IMPACT DC and PEPAC), as well as follow-up reminders for scheduling asthma care appointments with PCP and annual flu vaccines. Participants randomized to the control group will also receive reminder texts to schedule with their child's PCP and to get an annual flu shot. An algorithm of text message delivery will be determined for each participant (see appendix for Sample Algorithm content). The manual/intervention protocol and text messaging content will be refined and finalized during the start-up phase of the project (see Protection of Human Subject section for timeline). Within 24 hours of enrolling in the study, participants in the intervention will begin receiving a series of automated bidirectional text messages to their mobile phones based on the education components of IMPACT DC and PEPAC. In order to be oriented and familiar with the content of these messages participants randomized to intervention will also receive face-to-face PEPAC education, including the 3S tool kit card during their baseline visit. Messages will originate from the T2B program during the first 3 months, after which parents can text key words to repeat or receive additional messages/education at any time.

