	Identification of personal goals (tailored)	
 Fewer ED visits Missing less school Be more active Follow-up with PCP every 3 months 	
Facilitation	Education	
 2-3 messages/week – Personalized, Interactive Examples will be based on stated information and goals (personalized) Statement with response required about correct answer for example given (interactive) Asthma Education Example –Controller medications should be taken every day. Choose a time a day that you and [child's initials] will remember. Txt MEDS 4 info. Health Communication Example –Saying It Back is important 2 b sure you know your child's asthma plan. Txt 3SS for help on what to ask. 	3-12
	Reminder Messages	
 Reminder to follow-up with PCP, Influenza Vaccine Reminder Example –Time 4 [child's initials] 2 follow-up with PCP. Did u make an appt? Reply YES or NO. Reminder to schedule study follow up call 	
Self-efficacy	Keyword requests	
(3SS) –Info from communication toolkit (PCP) – Reminder of when to follow-up with PCP (GOAL) - Reminder of parent's intervention goals
 
(MEDS) – Info on difference between controller and rescue medications (TRIGGERS) – Info on common triggers
	13-52 or On demand

Participants will receive a handout with instructions on how to interact with the text message intervention (including opt-in instructions and numbers to call for problems). In addition, parents will be informed that the text messaging system is automated and their responses will be sent to a secured computer system so they should not send text messages seeking medical care. Should the participant send a text message to the system that does not align with the algorithm response programming, they will receive a standard message with instructions to contact the T2B team, their health care provider or 911 if it is an emergency. Research staff will also have the capacity to monitor participant engagement with the system to

troubleshoot any problems. Participants randomized to T2B, intervention, group will also receive a wallet sized “tool kit” reminding them of the 3 S’s and the key words to request text information.

REFERENCES CITED

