COVER PAGE

Text2Breathe: Enhance Parent Communication to Reduce Pediatric Asthma Disparities (T2B)

NCT03032159

July 10, 2014

C.5. Statistical Analyses

C.5.a: Preliminary Descriptive Analysis of Data

We will summarize all baseline variables overall and by study arm to assess the balance achieved by randomization and to check assumptions such as normality and equality of variances. The distributions of continuous variables will be summarized using means, standard deviations, medians, and ranges. Categorical variables will be summarized using frequency distributions. Non-parametric tests (e.g., Wilcoxon rank-sum and Fisher's exact) will be used in subsequent analyses as needed. Cronbach alpha reliabilities will be estimated for 12 all standardized instruments to assess whether the instruments are as reliable in our target population as in the population on which the instruments were validated. Frequency of missing data for each outcome variable will be determined at each time point. Baseline characteristics of missing and non-missing respondents at the 3, 6, 12 and 24 month time points will be compared to assess for attrition bias. We will employ multiple imputation to account for missing data, if necessary.^{84, 85} We will examine counts of mobile interactions captured by Rip Road (e.g., number of messages received and sent by each participant; See section 5.1.d.) to assess engagement with the intervention, overall and by participant characteristics.

C.5.b: Analysis Plan for Addressing Specific Aims

In **Aim 1**, to assess the intervention effect on the primary and secondary distal outcomes (i.e., the number of ED visits for asthma care during the 12-month interval following randomization, and the number of days of impairment during the two weeks prior to the 12-month interview, respectively), we will utilize negative binomial regression, a generalization of Poisson regression which yields unbiased inference even if the outcome variable is over-dispersed (i.e., the variance exceeds the mean) to estimate incidence rate ratios (IRRs) and 95% confidence intervals (CIs) for count data. The single independent variable in each model will be study group, and the exponentiated form of its regression coefficient will reflect the relative difference between groups in the annual rate of ED visits or frequency of impaired days.

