In prior studies, we have been able to maintain a 90% retention rate over a 6-month follow-up period. We will employ retention strategies that have been successful in this population in previous studies. Conservatively estimating a retention rate of 80% at the 12-month assessment, we must enroll 138 participants in each group (total N=276). The Seattle Children's ED currently serves approximately 1400 2-12 year old asthma patients per year, 40% (n=530) of whom are Medicaid insured. We estimate that 70% of this total will meet the remaining eligibility criteria (n=371). If 40% of these patients consent to the trial, which is much less than the 60-70% participation rates for Seattle Children's ED-based studies, we will yield our projected sample size of 276 in the proposed 24 month enrollment period. Thus, we estimate that we will need to approach 5-7 parents to recruit at least 3 participants per week, with an estimated recruitment of approximately 12 participants per month (minimum of 6 and maximum of 18 in any given month to assure there is not seasonal over-representation in the study sample).

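### The primary ED-visit count rests on 12-month recall by parents who can probably tell their arm, and the planned medical-record review feeds into no analysis that would show whether reporting differs by arm

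*Protocol*

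**What the plan says.** **Source of the count.** Under Data Collection (Distal Outcome Measures) the protocol states: "Parents will report whether and how many times their child was taken to the emergency room because of asthma during the past 12 months". The Outcomes paragraph of the protocol summary says outcome data "will be collected via structured telephone interviews".

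**Role of the medical record.** The same Data Collection entry continues: "We will validate a large portion of this data with EMR review". It explains that the two hospitals are the main EDs for young patients in Seattle and Tacoma. On reach, Data Collection says: "Electronic medical record review will be conducted by trained study staff at the site where the participant was enrolled". No rule says which source prevails when they disagree, or whether record counts are used when a parent is not interviewed.

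**Analysis.** SAP C.5.b defines the primary outcome as "the number of ED visits for asthma care during the 12-month interval following randomization", analysed by negative binomial regression with study group as the only independent variable. The SAP names no data source for the count and does not mention record review of outcomes. The planning rate of 1.28 visits per year in C.5.c does come from ED records.

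**What parents see.** Under Study Intervention, "participants randomized to intervention will also receive face-to-face PEPAC education", followed by interactive educational texts. Controls receive reminder texts only. Table 1 lists personal goals that T2B parents may choose, beginning "Fewer ED visits Missing less school Be more active".

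**Safeguards.** Follow-up interviewers are blinded unless no blinded interviewer is available, and unblinded interviews are documented. Non-contacts are emailed an online survey, and a missed wave does not end follow-up. SAP C.5.a compares baseline characteristics of missing and non-missing respondents and allows multiple imputation if needed. C.5.c plans on "Conservatively estimating a retention rate of 80% at the 12-month assessment".

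**The concern.** The people who supply the primary outcome can very probably tell which arm they are in, and some T2B parents will have chosen reducing that same outcome as their goal. If they recall or report a smaller share of their visits than control parents do, the shortfall looks like a treatment effect. Blinding the interviewer does not prevent this, because the respondent is the source. Imputation does not correct it either, because it fills in missing reports on the pattern of the reports that were given.

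The look-back raises a second, smaller problem. The 12-month call may be made up to a month either side of the due date (Retention and Compensation). Asked a month early, a question about the past 12 months reaches back before randomisation and can take in the enrolment ED visit, which every child had. Asked a month late, it leaves out the first month after randomisation. The SAP interval starts at randomisation, so the question and the endpoint do not cover the same period. Visits in the record are dated.

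At stake is what a positive result could support. Without a prespecified record-based analysis, fewer visits cannot be separated from fewer reported visits. A record analysis added after the results are known would carry less weight.

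**Working it through.** **Inputs from SAP C.5.c.** Control rate 1.28 per year; 35% reduction, so T2B rate 1.28 × 0.65 = 0.832; two-sided alpha 0.05; 125 per group for at least 90% power; analytic sample 110; retention 80%. The negative binomial dispersion k is not stated, so a range is shown.

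**1. The plan's own figures.**
- Enrolment: 110 / 0.80 = 137.5, rounded up to 138 per group, 276 in total. This matches the SAP. It leaves 138 − 110 = 28 per group without a 12-month parent report.
- Power, Wald test on the log rate ratio: SE² = (1/m0 + 1/m1 + 2k)/n. With k = 0 and n = 125: (0.7813 + 1.2019)/125 = 0.01587, SE = 0.126, |ln 0.65|/SE = 0.4308/0.126 = 3.42, power 92.8%. This agrees with the stated 90% or more.
- Power of exactly 90% at 125 corresponds to k of about 0.11. At 110 per group, power is 89.4% (k = 0), 86.0% (k = 0.11) and 80.0% (k = 0.31).

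**2. Effect of differential reporting when T2B does nothing.** Let T2B parents report a fraction r of what controls would report for the same use. The expected rate ratio is then r, and the rejection probability is Φ(−1.96 − ln r/SE) + Φ(−1.96 + ln r/SE), with SE² = (1/1.28 + 1/(1.28r) + 2k)/110.

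Example with r = 0.90, k = 0: SE² = (0.7813 + 0.8681)/110 = 0.01499, SE = 0.1224, ln 0.90/SE = −0.1054/0.1224 = −0.86, rejection 13.8%.

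| Assumed under-reporting in T2B | k = 0 | k = 0.11 | k = 0.5 |
|---|---|---|---|
| none | 5% | 5% | 5% |
| 10% | 13.8% | 12.7% | 10.4% |
| 15% | 25.7% | 23.3% | 17.9% |

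If the true rate ratio were 0.65, 10% under-reporting in T2B would move the expected estimate to 0.65 × 0.90 = 0.585. The opposite error, controls reporting 10% fewer, would move it to 0.65/0.90 = 0.72.

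**3. Effect of counting the enrolment visit.** If a share p of parents in both arms include it, the planned ratio becomes (0.832 + p)/(1.28 + p), ignoring the month of follow-up lost by an early call. With p = 0.25 (assumed) this is 1.082/1.53 = 0.71. This error pulls towards no effect.

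**4. What records would do for precision.** Using all 138 instead of 110 multiplies the standard error by √(110/138) = 0.893, an 11% reduction, only if records capture every visit. If they capture a share c equally in both arms, then under no effect the multiplier is √[(110/138) × (1/(1.28c) + k)/(1/1.28 + k)]. At c = 0.80 this is 0.998 (k = 0), 0.986 (k = 0.11) and 0.958 (k = 0.5), a gain of about 0 to 4%. At c = 0.70 and k = 0 it is 1.067, a loss. The capture share is an assumption, because the protocol says only that a large part can be checked. Equal capture leaves the rate ratio unbiased.

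**The case against.** The plan does more than a quick reading suggests. Interviewers are blinded where possible. Retention is supported by alternative contacts, an emailed survey and continued calls, and the ED question is asked at every wave. Imputation is available. A reader might infer that the planned 20% loss passes untouched into the primary estimate. The documents do not support that: 20% is a cautious planning figure, and missing data have a stated, though conditional and unspecified, treatment.

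A reader might also infer that the T2B texts are built around reducing ED visits. That is one of four listed goals. Parents choose, and the chosen goal shapes only part of the communication content. Awareness of arm is itself an inference from what each arm receives; no passage states what parents are told. The bias could run the other way if education makes parents notice and report more visits.

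Records have their own gaps. Review is described at the enrolling site only, other EDs are invisible, and in a population the protocol calls transient, a family that has moved away would be recorded as having no visits.

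All of this stands. It limits the size of the claim and rules out treating the record as the truth. It does not remove the gap: none of these safeguards acts on differential reporting by parents, and the one data stream that could reveal it is used in no planned analysis.

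**Conclusion.** The concern holds as a gap in the analysis plan, not as evidence of bias. Under an assumed 10% shortfall in T2B reporting and no true effect, the false-positive rate is about 10–14% instead of 5%, for k from 0.5 down to 0. It is about 18–26% at 15%. These figures rest on 110 analysed per group, a mean of 1.28 and a Wald test. The size and direction of any real reporting difference cannot be derived from the documents.

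Two stronger conclusions are tempting. The first is that the primary count should be rebuilt as record visits plus parent-reported visits to other EDs. The protocol describes no question on which ED was visited, non-responders would be counted differently from responders, and the added part would keep the same reporting problem. The second is that a record analysis would buy an 11% smaller standard error. That needs full capture, and near 80% capture the two sources are about equal. The reason to act is protection against bias.

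**What to change.** Keep parent report as the primary source and say so in SAP C.5.b. Add there:

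1. A prespecified sensitivity analysis that repeats the primary negative binomial model on asthma ED visits identified in the medical record, dated after randomisation through day 365 and excluding the enrolment visit.
2. Inclusion of all 276 randomised children, including those whose parents miss the 12-month interview.
3. Abstraction blind to study arm, at the enrolling site and at both hospitals where access allows.
4. A table of parent–record agreement by arm.
5. A statement, given with the result, that records miss visits to other EDs and show false zeros for families who have moved away.

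**Cost.** SAP wording, and abstraction extended to non-responders (about 28 per group at the planned retention) and, where possible, to the second hospital. Record review is already planned, so no new data source is needed and the primary analysis does not change.
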